Anterior cruciate ligament reconstruction utilizing a hamstring autograft is a surgical technique that has gained popularity among orthopedic surgeons caring for adolescent patients. While utilization of a hamstring autograft is a revered technique, harvest of the hamstring yields significant pain. Sciatic peripheral nerve blockade has proven to reliably provide analgesia at the hamstring donor site. Single-injection sciatic peripheral nerve blockade is considered a basic and effective technique, making its use following anterior cruciate ligament reconstruction standard practice in many institutions. The duration of action of single-injection sciatic peripheral nerve blockade may fail to outlast the pain arising from the hamstring donor site, prompting some clinicians to employ continuous sciatic peripheral nerve blockade via an indwelling catheter. A lack of comparative effectiveness studies exists in the literature regarding the duration of action of peripheral nerve blockade necessary to adequately provide pain control following hamstring autograft harvest, resulting in disagreement among clinicians as to best pain control practices. Proponents of continuous sciatic peripheral nerve blockade assert that while more costly, the extended duration of analgesia afforded by this technique improves pain control postoperatively and decreases the use of other pain medications. Advocates of single-injection sciatic peripheral nerve blockade cite concerns associated with continuous sciatic peripheral nerve blockade known to be detrimental to rehabilitation, such as decreased active knee flexion and increased risk of falls. The purpose of this research is to compare the effect of single-injection sciatic PNB to continuous sciatic PNB on 1) postoperative pain control as measured by self-reported pain scores, pain medication use, and unplanned hospital admission due to poor pain control, 2) active knee flexion, and 3) patient satisfaction with pain control following ACL reconstruction with a hamstring autograft. The findings of this study have the potential to guide informed clinical reasoning and decision making regarding sciatic peripheral nerve blockade techniques following hamstring autograft harvest in adolescents undergoing anterior cruciate ligament reconstruction.

I. BACKGROUND AND SIGNIFICANCE

Anterior cruciate ligament (ACL) injury is the most prevalent injury treated in orthopedic sports medicine. The incidence of ACL injuries continues to increase with approximately 250,000 now occurring annually in the United States (Gagnier, Morgenstern, & Chess, 2012). As such, ACL reconstruction has become a common surgical procedure and is frequently performed on an outpatient basis. ACL reconstruction has historically been avoided in skeletally immature patients due to concerns of injuring the immature physes, resulting in growth deformities. Adolescents with ACL injuries were typically treated conservatively, with many orthopedic surgeons relying on non-surgical techniques, such as bracing and activity restrictions, for treatment. Advances in surgical techniques, however, now allow ACL reconstruction to be performed safely and effectively in skeletally immature patients. Subsequently, the incidence of ACL reconstruction in the adolescent population has increased approximately 300 percent in the last two decades.

Currently the mean age of ACL reconstruction is 18 years indicating half of the number of patients undergoing ACL reconstruction are adolescents (Silvers & Mandelbaum, 2007). Given the decreasing age of patients now undergoing this surgical procedure, orthopedic surgeons are charged with ensuring optimal ACL longevity following reconstruction.

Several options exist for replacement of the damaged ligament during ACL reconstruction in adolescents, yet the use of a hamstring autograft has emerged as the technique of choice due to the overall decreased morbidity and proven long-term stability when compared to other ligament reconstruction options (Mehta, Mandala, Foster, & Petsche, 2010; Pallis, Svoboda, Cameron, & Owens 2012). As such, there has been a marked increase in the use of hamstring autografts for reconstruction of the injured ACL in adolescents due to the favorable long-term outcome profile of this surgical technique when compared to other available graft reconstruction options. The growing trend to use a hamstring autograft for ligament reconstruction is a departure from the technique typically employed in the adult population, where use of an allograft tendon, or transplant tendon from another individual, has been the predominant technique employed. The use of hamstring autograft creates new concerns for surgeons and anesthesiologists alike, as this technique is known to lead to significant pain at the hamstring donor site during the postoperative period. The significance of the pain secondary to hamstring autograft harvest remains undetermined beyond the initial 24 hours postoperatively, however, as it has yet to be fully investigated (Bushnell, Sakryd, & Noonan, 2010). The harvesting of a hamstring autograft, however, yields significant postoperative pain for which no consensus exists among clinicians as to how to best treat.

Sciatic peripheral nerve blockade (PNB) has proven to abate hamstring donor site pain in a reliable fashion while avoiding undesirable opioid-related side

effects (Bushnell, Sakryd, & Noonan, 2010). The efficacy of sciatic PNB can be attributed to the origin of pain following hamstring autograft harvest, graft fixation, or both, which lies in the sciatic nerve distribution (Frost, Grossfeld, Kirkley, Litchfield, Fowler, & Amendola, 2000). Controversy remains as to whether single-injection or continuous sciatic PNB is most appropriate following ACL reconstruction with a hamstring autograft. Single-injection sciatic PNB is a regional anesthetic technique employed to anesthetize the sciatic nerve with a single dose of local anesthetic. This technique offers pain control for a limited amount of time based on the volume and concentration of local anesthetic used. Continuous sciatic PNB entails placing a continuous perineural infusion (CPI) catheter so that local anesthetic may be released slowly but continuously adjacent to the sciatic nerve (perineural) for several days postoperatively. While both techniques of sciatic PNB alleviate pain in the immediate postoperative period, only continuous PNB has the ability to reliably provide analgesia on subsequent postoperative days.

No consensus exists regarding the duration of sciatic PNB necessary to effectively provide pain control following ACL reconstruction with a hamstring autograft. The disagreement among clinicians as to best practices of pain control following ACL reconstruction with a hamstring autograft is largely due to the lack of evidence comparing single-injection and continuous sciatic PNB following hamstring autograft harvest. Mismanagement of pain can be detrimental, resulting in negative physiological, psychological, and economic consequences (Agin & Glass, 2005). Failure to address pain may lead to future impairment in functioning as well as heighten anxiety and fear, which in turn may further increase the perception of pain (Matthews, 2011). Continued mismanagement of pain results in increased suffering and misery that can ultimately impact one's lifestyle and personality (Beales, Holt, Keen & Mellor, 1983). In addition, unaddressed pain can cause great disruption to families caring for patients. From an economic perspective, the mismanagement of pain can lead to slower rates of recovery, resulting in increased healthcare-related costs and time away from school and work (Twycross, 2002).

There is evidence that sciatic PNB, regardless of technique, significantly reduces pain when compared to intravenous opioids during the initial 24-hour postoperative period following knee surgery (Wegener, van Ooij, van Dijk, Hollmann, Preckel, & Stevens, 2011). As such, single-injection sciatic PNB, which can last up to 24 hours, should provide adequate analgesia precluding the need for oral narcotic or nonsteroidal anti-inflammatory medications following ACL reconstruction with a hamstring autograft. It remains unknown, however, if any benefit is gained during the initial 72-hour postoperative period from extending analgesia for the hamstring donor site via continuous sciatic PNB. While continuous sciatic PNB with a CPI catheter extends the duration of analgesia, it also extends the duration of anesthesia potentially leading to a decrease in motor function and subsequently active knee flexion. The sciatic nerve innervates the hamstrings, which are responsible for knee flexion (Distad &

Weiss, 2013). The decrease in active knee flexion may impede the ability of the patient to begin rehabilitation on the first postoperative day. This is an important consideration because early rehabilitation, which includes contraction of the quadriceps and hamstring muscles as well as weight bearing exercises with the aid of crutches, leads to faster recovery of long-term range of motion and a lower incidence of knee laxity following ACL reconstruction when compared to delayed rehabilitation (Shaw, Williams, & Chipchase, 2005; Pinczewski et al., 2007). Determining the duration of sciatic PNB required to effectively control pain following ACL reconstruction with a hamstring autograft, without impeding active knee movement, will help define best practice going forward.

II. RESEARCH QUESTION

This study aims to answer the following research question: Does the duration of sciatic PNB impact the ability to effectively provide postoperative pain control following ACL reconstruction with a hamstring autograft in the adolescent population?

III. PURPOSE OF THE STUDY

The purpose of this research is to compare the effect of single-injection sciatic PNB to continuous sciatic PNB on 1) postoperative pain control as measured by self-reported pain scores, pain medication use, and unplanned hospital admission due to poor pain control, 2) active knee flexion, and 3) patient satisfaction with pain control following ACL reconstruction with a hamstring autograft. The results of this research have the potential to positively impact pain control for the adolescent population undergoing this surgical procedure and foster responsible utilization of limited resources.

SPECIFIC AIM 1. The first aim of the study is to explore the impact of sciatic PNB technique on hamstring donor site pain control postoperatively.

H1.a. The extended duration of analgesia offered by continuous sciatic PNB decreases pain scores during the initial 72 hours following hamstring autograft harvest when compared to single-injection sciatic PNB.

H1.b. The extended duration of analgesia offered by continuous sciatic PNB decreases oral pain medication use during the initial 72 hours following hamstring autograft harvest when compared to single-injection sciatic PNB.

H1.c. The extended duration of analgesia offered by continuous sciatic PNB decreases the incidence of unplanned admission due to poor pain control during the initial 72 hours following hamstring autograft harvest when compared to single-injection sciatic PNB.

SPECIFIC AIM 2. The second aim of the study is to explore the impact of sciatic PNB technique on active knee flexion postoperatively.

H2. The extended duration of analgesia offered by continuous sciatic PNB does not delay active knee flexion during the initial 72 hours following hamstring autograft harvest when compared to single-injection sciatic PNB.

SPECIFIC AIM 3. The third aim of the study is to explore the impact of sciatic PNB technique on patient satisfaction with postoperative pain control.

H3.1. The extended duration of analgesia offered by continuous sciatic PNB improves patient satisfaction during the initial 72 hours following hamstring autograft harvest when compared to single-injection sciatic PNB.

IV. PREVIOUS CLINICAL EXPERIENCE

Concurrent Research Studies: The Department of Anesthesiology is not currently conducting another protocol with this patient population.

By the Investigator: This investigator currently is conducting research regarding the efficacy of regional anesthetic techniques at Cincinnati Children's Hospital Medical Center (CCHMC). Recruitment for an IRB-approved study comparing the efficacy of ultrasound-guided transversus abdominis plane blockade with surgeon performed ilioinguinal/iliohypogastric blockade following unilateral inguinal herniorrhaphy is on-going.

By Other Investigators: Sciatic PNB has been reported to most reliably decrease hamstring donor site pain, however, there remains no consensus as to the duration of action required to effectively control donor site pain throughout the postoperative period (Tran, Ganley, Wells, Ganesh, Minger, & Cucchiaro, 2005; Bushnell, Sakryd, & Noonan, 2010).

To date, there has only been one study reported in the literature comparing single-injection and continuous sciatic PNB. Continuous sciatic PNB was reported to offer significant advantages in pain control for adults only during the initial 24 hours following knee surgery (Wegener, van Ooij, van Dijk, Hollmann, Preckel, & Stevens 2011). It should be noted, however, this study does not refer to ACL reconstruction, rather the study population is comprised of patients undergoing total knee replacement making it challenging to appropriately translate and apply the clinical knowledge gained from that study to other clinical scenarios.

V. STUDY DESIGN

This study employs an experimental posttest-only design with repeated follow-up, with the gate control theory of pain serving as the theoretical foundation. An experimental posttest-only design with repeated follow-up is appropriate for this study, as the outcome is not relevant until after the intervention is complete. This

study is a randomized prospective observational study to compare the effect of single-injection sciatic PNB to continuous sciatic PNB on postoperative pain control, active knee flexion, and patient satisfaction with pain control following ACL reconstruction with a hamstring autograft.

A. Study Protocol:

The intervention in this study will be one of two techniques for sciatic PNB: single-injection PNB or continuous sciatic PNB with a CPI catheter. The PNB protocol will be assigned by computer-generated randomization. All study participants will receive standard care, including standard anesthetic care as recommended by the American Society of Anesthesiologists and the American Association of Nurse Anesthetists, and the surgical procedures will be in accordance with those set forth by the American College of Surgeons. Anesthetic management will be left to the discretion of the clinical team providing anesthesia care, which includes, but is not limited to, the amount of inhalation anesthetic and intravenous opioids each study participant receives throughout the intraoperative portion of the study.

All sciatic PNB will be performed following the induction of general anesthesia, but prior to the end of anesthesia. For patients randomized to the single-injection sciatic PNB group, ultrasound will be utilized to identify the sciatic nerve in the sub-gluteal region. Once the sciatic nerve is identified, 1 mL/kg (to a maximum volume of 20 mLs) of 0.2% ropivacaine without epinephrine will be injected into the perineural space surrounding the sciatic nerve.

For patients randomized to the continuous sciatic PNB group, ultrasound will be utilized to assist the anesthesia team with placing the catheter tip adjacent to the sciatic nerve in the sub-gluteal region in preparation for continuous infusion of local anesthetic postoperatively. Once proper placement of the sciatic CPI catheter is verified, 1 mL/kg (to a maximum volume of 20 mLs) of 0.2% ropivacaine without epinephrine will be administered incrementally over two minutes. An infusion of 0.125% ropivacaine will be started at the end of surgery at a rate of 3-4 mL/hr (based on patient weight) for 48 hours postoperatively. While assessments will be made through 72 hours postoperatively, CPI catheters will only remain in-situ for 48 hours, as the incidence of infection increases should an indwelling CPI catheter remain greater than 48 hours (Jeng, Torrillo, & Rosenblatt, 2010).

Following sciatic PNB, continuous femoral PNB will be performed. Patients in both study groups will receive continuous femoral PNB with a CPI catheter to provide analgesia to the anterior aspect of the knee, as this is an accepted standard of practice following ACL reconstruction. Ultrasound will be utilized to assist the anesthesia team with placing the catheter tip adjacent to the femoral nerve in the inguinal region in preparation for continuous infusion of

local anesthetic postoperatively. Once proper placement of the femoral CPI catheter is verified, 1 mL/kg (to a maximum volume of 20 mLs) of 0.2% ropivacaine without epinephrine will be administered incrementally over two minutes. An infusion of 0.125% ropivacaine will be started at the end of surgery at a rate of 6-8 mL/hr (based on patient weight) for 48 hours postoperatively.

The recommended dosing range of ropivacaine is 0.2-0.4 mg/kg/hr (Chelly, 2009). Therefore, patients weighing 60 kg or more will receive infusions of 0.125% ropivacaine at a rate of 8 mL/hr via the femoral CPI catheters and a 0.125% ropivacaine at a rate of 4 mL/hr via the sciatic CPI catheter (as applicable). Patients weighing less than 60 kg will receive an infusion of 0.125% ropivacaine at 6 mL/hr via the femoral CPI catheter and 3 mL/hr via the sciatic CPI catheter (as applicable). These parameters ensure that the total local anesthetic dose remains within the recommended dosing guidelines should a patient be randomized to receive both continuous femoral PNB and continuous sciatic PNB. In addition, establishing weight based infusion rates allows for the study group receiving one CPI catheter and the group receiving two CPI catheters to be as similar as possible thereby improving the ability to compare the outcomes of each study group.

Patients will not be blinded as to what study group they have been randomized to participate in. Blinding of subjects can be beneficial in studies because it minimizes the introduction of biases stemming from awareness. Blinding is not always possible, however. For example, in this study it would be challenging to blind subjects to the sciatic nerve block treatment group, as one group will have an indwelling sciatic CPI catheter and the other will not. One means of blinding study participants would be to insert sciatic CPI catheters in all patients and infuse local anesthetic in one group and a placebo in the other group, however, the costs and potential risks, such as opportunity for infection, potential tissue damage and potential for abscess formation secondary to infusion of a placebo, makes blinding of study participants prohibitive.

1. Sciatic Peripheral Nerve Blockade Description:

Under ultrasound-guidance, the sciatic nerve can readily be identified in the posterior thigh. The nerve appears hyperechoic and can be traced distally to the popliteal fossa, where it divides into the tibial and common peroneal nerves. Local anesthesia is injected under real-time visualization following a negative aspiration. If a single-injection block is done, local anesthesia is deposited adjacent to the sciatic nerve within the fascial plane, but not within the epineurium. Should a CPI catheter be placed, the CPI catheter will be placed under ultra-sound guidance, with the tip of the catheter being placed immediately adjacent to the sciatic nerve, after the local anesthesia has been deposited.

Peripheral Nerve Blockade Related Risks: While the general risks for peripheral nerve blockade apply to femoral and sciatic nerve blockade, the site of injection for these blocks is considered relatively low risk. The risks of the drug in the current study are no different than would be expected when the drug is used in any other local infusion. As with any local anesthetic drug, high doses or unintentional intravascular injection may lead to high plasma levels and related myocardial depression, decreased cardiac output, heart block, hypotension, bradycardia, ventricular arrhythmias, including ventricular tachycardia and ventricular fibrillation, and possibly cardiac arrest.

Risks related to the drug utilized in the current study ropivacaine are characteristic of those associated with other amide-type local anesthetic drugs, which include:

- Urticaria
- Pruritus
- Erythema
- Angioneurotic edema
- Tachycardia
- Sneezing
- Nausea
- Vomiting
- Elevated temperature
- Possibly anaphylactoid symptomology

Additionally, there is a low risk of mild discomfort or inconvenience to the subject, as they will receive regional blockade of some nature. Additionally, unforeseen risks may include, but are not limited to:

- Needle trauma
- Intraneural injection
- Intravascular injection
- Local anesthetic toxicity
- Hematoma
- Infection
- Poor/failed block

Finally, risks related to the use of a CPI catheter are rare, but include:

- Infection
- Infusion pump malfunction
- Local anesthetic toxicity
- Skin irritation or allergic reaction secondary to dressing material
- Unintentional CPI catheter dislodgement

- Fluid (local anesthetic) leakage at the CPI catheter insertion site
- Falls secondary to motor blockade

2. Risk Benefit Analysis:

Benefits: Subjects in this research study are unlikely to gain any personal benefit on the day of the study from their participation as the decisions of the clinical team caring for the patients will be guided by the randomized study protocol. The knowledge gained may be of benefit in the management of future adolescent patients who require ACL reconstruction. The ability to effectively provide pain control will lead to more efficient utilization of healthcare resources.

Study Related Risks: The risks associated with this study are minimal and are related to PNB. Both techniques of sciatic PNB included in this study are accepted techniques in clinical practice. All risks related to sciatic PNB are incidental, that is, associated with PNB, not the study itself as this is an observational study.

Risks/Benefit Analysis: It is the opinion of the principal investigator (PI) that this study is classified as “minimal risk but without direct benefit to participants”.

B. Subject Population:

A subject may be INCLUDED in this study if:

1. The subject is male or female;
2. The subject is of any racial or ethnic group;
3. The subject is age 10 years to 18 years (inclusive);
4. The subject is scheduled for the following:
Unilateral ACL reconstruction with a hamstring autograft under general anesthesia on an outpatient basis, and not being performed in conjunction with any other surgical procedures;
5. The subject is American Society of Anesthesiologists (ASA) patient classification I-II;

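### The two-tier infusion rates do not keep the two-catheter ropivacaine dose within the protocol's own 0.2-0.4 mg/kg/hr range: it is above 0.4 for any patient below 28.125 kg, and no minimum weight or per-kilogram cap prevents this (minor)

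*Combined protocol and SAP*

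**What the plan says.** All of the dosing text is in section V.A, Study Protocol, of the combined protocol and SAP.

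- Reference range: "The recommended dosing range of ropivacaine is 0.2-0.4 mg/kg/hr".
- Lower tier: "Patients weighing less than 60 kg will receive an infusion of 0.125% ropivacaine at 6 mL/hr via the femoral CPI catheter and 3 mL/hr" through the sciatic catheter where there is one. The tier has no lower weight limit.
- Upper tier, 60 kg or more: 8 mL/hr femoral and 4 mL/hr sciatic, at the same concentration.
- Who has both catheters: "Patients in both study groups will receive continuous femoral PNB with a CPI catheter". The continuous arm adds the sciatic catheter, so only that arm has two infusions.
- Duration: the sciatic infusion "will be started at the end of surgery at a rate of 3-4 mL/hr (based on patient weight) for 48 hours postoperatively". The femoral infusion also runs for 48 hours.
- Assurance: "These parameters ensure that the total local anesthetic dose remains within the recommended dosing guidelines should a patient be randomized to receive both" continuous blocks.

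Section V.B admits patients aged 10 to 18 in ASA class I or II. It sets no minimum weight or BMI.

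**The concern.** The assurance is categorical and concerns a dose per kilogram, but the rates are fixed in mL/hr. A fixed rate limits the absolute dose only. The dose per kilogram rises as weight falls, and nothing in the lower tier stops that rise. A per-kilogram guarantee therefore needs either a floor on weight or a cap on the rate, and the plan has neither.

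What is at stake is a dosing statement that the trial relies on for minors, where randomization decides who receives the second infusion. Clinicians told that the rates guarantee compliance have no prompt to check the dose for a very light patient.

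**Working it through.** **Inputs, all from section V.A.** Concentration 0.125%, which is 1.25 mg/mL. Rates: 6 + 3 mL/hr below 60 kg and 8 + 4 mL/hr from 60 kg. Range: 0.2-0.4 mg/kg/hr. Duration: 48 hours.

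**Formulas.** Dose rate = total mL/hr × 1.25 / weight. Threshold weight = total mg/hr / limit in mg/kg/hr.

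**Where the plan's statement reproduces.**

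- Below 60 kg: 9 × 1.25 = 11.25 mg/hr. The total is 0.4 at 11.25/0.4 = 28.125 kg and 0.2 at 11.25/0.2 = 56.25 kg.
- From 60 kg: 12 × 1.25 = 15 mg/hr. The total is 15/60 = 0.25 at 60 kg and 0.2 at 15/0.2 = 75 kg. It is never above 0.4 in this tier.

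So the two-catheter total lies inside the range for 28.125-56.25 kg and for 60-75 kg.

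**Where it does not.**

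| Weight | Two-catheter total (mg/kg/hr) | Position |
|---|---|---|
| 25 kg (illustrative) | 11.25/25 = 0.450 | above 0.4 by 12.5% |
| 27 kg (illustrative) | 11.25/27 = 0.417 | above 0.4 by 4.2% |
| 28.125 kg | 0.400 | at the upper end |
| 59.9 kg | 11.25/59.9 = 0.188 | below 0.2 |
| 80 kg | 15/80 = 0.188 | below 0.2 |

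**Over the full infusion.** The lower tier delivers 11.25 × 48 = 540 mg. The upper end of the range corresponds to 0.4 × 27 × 48 = 518.4 mg at 27 kg (21.6 mg less) and 0.4 × 25 × 48 = 480 mg at 25 kg (60 mg less).

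**Single-injection arm.** Femoral only, below 60 kg: 6 × 1.25 = 7.5 mg/hr, which is above 0.4 only below 7.5/0.4 = 18.75 kg. It is already below 0.2 above 7.5/0.2 = 37.5 kg.

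**Size of the cap.** 0.4/1.25 = 0.32 mL/kg/hr. At 28.125 kg this is 9.0 mL/hr, the rate already ordered. At 27 kg it is 8.64 mL/hr and at 25 kg 8.0 mL/hr.

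**The case against.** The strongest case against the point is that it may concern nobody. It needs a patient aged at least 10, under 28.125 kg, having outpatient hamstring-autograft reconstruction and randomized to the continuous arm. The documents call the population adolescent throughout and give no weight distribution. The aim in section V.C of enrolling physically varied subjects is weak evidence that such a patient would appear. This objection stands and limits the severity, but it does not make the assurance true.

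A second objection is that clinicians can intervene: "Anesthetic management will be left to the discretion of the clinical team providing anesthesia care". That clause is open-ended, and so is the fifth exclusion criterion in section V.B, under which the investigator could leave out a very small child. However, the examples in the first clause are intraoperative inhaled agents and opioids, while the infusion starts at the end of surgery. The examples in the exclusion do not include low weight. Neither clause sets a dose.

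Three stronger readings are tempting, and the documents do not support them.

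- A reader might infer that 0.4 mg/kg/hr is a hard safety limit. Section V.A presents it as the top of a recommended range, and the source cited for it cannot be consulted here.
- A reader might infer a demonstrated cardiac hazard, because section V.A.1 warns that "high doses or unintentional intravascular injection may lead to high plasma levels and related myocardial depression". That warning names no threshold and is not tied to 0.4 mg/kg/hr.
- A reader might contrast the infusion with the boluses, which appear to be scaled to weight: "1 mL/kg (to a maximum volume of 20 mLs) of 0.2% ropivacaine without epinephrine will be administered incrementally over two minutes". From 20 kg upward that rule gives a flat 20 mL, so the contrast is empty at the weights discussed.

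Nor should the shortfall below 0.2 be read as underdosing. The femoral-only arm is below that figure for most of the weight range, which suggests that the authors did not treat it as a required minimum.

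**Conclusion.** The assurance is wrong as written. On the protocol's own figures, the two-catheter infusion is above the upper end of the recommended range for any eligible patient under 28.125 kg, and nothing in the plan excludes such a patient or caps the rate. The excess is modest at the illustrative weights: 4.2% at 27 kg and 12.5% at 25 kg. Patients at 28.125 kg or more are never above 0.4 mg/kg/hr. Because the total also drops below 0.2 in two weight bands, the plan should not claim that the dose stays inside the full range.

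The threshold is exact arithmetic and assumes only that the stated concentration and rates are followed. The practical effect is uncertain, because the number of patients affected is unknown and may be zero. Sample size, endpoints and tests do not depend on this point. Severity is minor.

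**What to change.** Add one sentence to the infusion paragraph in section V.A:

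*The combined femoral and sciatic infusion must not exceed 0.4 mg/kg/hr (0.32 mL/kg/hr of 0.125% ropivacaine).*

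The clinical lead and pharmacy should decide how any reduction is split between the two catheters.

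Replace the assurance with one that the capped rates can meet:

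*With this cap, the total infusion dose does not exceed the upper end of the recommended range (0.4 mg/kg/hr) when both catheters are in use.*

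The cost is a short protocol amendment and a lower rate for continuous-arm patients under 28.125 kg only, for example 8.0 instead of 9 mL/hr in total at 25 kg. Dosing for everyone else is unchanged.
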